2. STUDY DESCRIPTION

2.1. Study Design

This Phase 2b study is a six-arm, multicenter, randomized, double-blind, placebo-controlled, and parallel-design trial of the safety and efficacy of cytisine in adult cigarette smokers who are willing to set a quit date that is 5-7 days after being randomized on the study. A total of 250 subjects are planned to be randomized at the ratio 2:1 to cytisine treatment and the respective placebo treatment as designated by the protocol defined schedule (i.e. the commercial titrated schedule vs the simplified three times daily (tid) schedule) for 25 days. Subjects will be stratified at randomization based on BMI class (18.5 to <25 kg/m²; 25 to <30 kg/m²; 30 to <35 kg/m²) as defined in the protocol. The six treatment arms will be:

Figure 1: Study Design Overview

The study will be comprised of a pre-study screen, followed by twenty-five (25) days of study treatment, an end-of-treatment visit at Week 4 (Day 27 ± 2 days), and weekly post-treatment follow up visits from Week 5 to Week 8 post-randomization.

Blinding

- The study will be double-blinded to dose (1.5 mg cytisine, 3.0 mg cytisine, placebo) but not to the administration schedule (commercial titration schedule, simplified tid schedule).
- Sponsor and contract research personnel responsible for collecting, monitoring and analyzing the study data will also be blinded to dose but not to administration schedule.
- In order to blind the study treatment dose, all subjects will take 2 tablets at every scheduled dosing. Subjects randomly assigned to Arm A or Arm D will take one 1.5 mg cytisine tablet and one placebo tablet at each dosing. Arm B or Arm E subjects will take two 1.5 mg cytisine tablets at each dosing. Arm C and Arm F subjects will receive two placebo tablets at each daily scheduled dosing to correspond to cytisine dosing.

Randomization

- Eligible subjects will be randomized 2:1 in a blinded manner to either Arm A or Arm B vs Arm C (2:1 randomization) or Arm D or Arm E vs Arm F (2:1 randomization)

- Subjects will be stratified at randomization by BMI class (18.5 to <25 kg/m²; 25 to <30 kg/m²; 30 to <35 kg/m²).
- Unique subject number and randomization code will be assigned to each study subject
- Parallel group design

Multicenter Trial

- This study will be conducted at multiple sites across the US

Type of Comparison

- Superiority in favor of cytisine

2.2. Treatment Schedules

For the 25-day commercial titration schedule, study drug will be administered according to the following schedule:

Treatment Day	Daily Administration	Approximate Interval
1-3	6 times daily	2 hours
4-12	5 times daily	2.5 hours
13-16	4 times daily	3 hours
17-20	3 times daily	4-5 hours
21-24	2 times daily	6 hours
25	1 time only	-

For the tid schedule, study drug will be administered according to the following schedule:

Treatment Day	Daily Administration	Approximate Interval
1-20	3 times daily	4-5 hours
21-24	2 times daily	6 hours
25	1 time only	-

All subjects will receive 2 tablets for each dose according to their randomization arm.

Subjects that work overnight will potentially be taking their daily administered dose over two calendar days. This is accounted for in the CRF and the date of their first dose taken will be recorded as the dosing start date.

2.3. Study Population

Approximately 250 subjects who are daily cigarette smokers intending to make a quit attempt during the study will be enrolled at multiple study sites within the US. Based on the planned 2:1 (cytisine:placebo) randomization, it is expected that 200 subjects will be randomized to receive

cytisine (50 subjects at each cytisine treatment arm) and 50 subjects will be randomized to receive placebo (25 subjects per treatment schedule).

3. STUDY OBJECTIVES

3.1. Primary Efficacy Objectives

The primary efficacy objectives of this study are:

1. Assess whether subjects randomized to cytisine, administered using the commercial titration schedule, have a greater overall reduction in cigarette smoking during the study treatment period (Day 1 – 25) compared to subjects randomized to the same titration schedule of a placebo.
2. Assess whether subjects randomized to cytisine, using a simplified tid schedule, have a greater overall reduction in cigarette smoking during the study treatment period (Day 1 - 25) compared to subjects randomized to the same tid schedule of a placebo.

3.2. Other Efficacy Objective(s)

Each of the following will include comparisons for 1.5 mg or 3.0 mg doses versus placebo when given as the commercial 25-day titration schedule and for the tid treatment schedule (as well as comparisons between the commercial 25-day titration versus tid treatment schedules). The other efficacy objectives are:

1. Assess the probability of abstinence from Week 5 to Week 8 post-randomization in subjects randomized to cytisine as compared to subjects randomized to placebo.
2. To compare cytisine and placebo arms on initial quit rates during study treatment, at Week 4 (End of Treatment) and on 7-day point prevalence abstinence at Week 5, Week 6, Week 7, and Week 8.
3. Among subjects abstinent at Week 4 (End of Treatment), compare time to failure to maintain abstinence through Week 8 between arms.
4. To explore potential relationships between subject-reported outcomes (e.g. anxiety, withdrawal symptoms, depression, tobacco craving, alcohol use) with the reduction in cigarette smoking during the study treatment period, as well as smoking cessation outcomes at Week 4 (End of Treatment) and from Week 5 to Week 8 post-randomization.
5. To explore a potential correlation for subject's nicotine metabolite ratio (NMR) with the reduction in cigarette smoking and smoking cessation outcomes.

3.3. Safety Objective(s)

To evaluate overall safety profiles of cytisine when administered at 1.5 mg or 3.0 mg, using the commercial 25-day titration or simplified tid schedules, compared to placebo.

3.4. Subject Selection

Only adult subjects (aged at least 18 years old) who are daily smokers (10+ cigarettes daily) with intention to quit smoking during the study, in addition meeting all the inclusion criteria and none of the exclusion criteria in the protocol will be enrolled in this study.

3.5. Determination of Sample Size

The sample size was computed based on data from a previous Phase 1/2 trial and for achieving narrow confidence intervals (CI) for the primary comparison estimates in this trial.

The trial size was based on projected realization of the effect size estimate for the primary outcome based on data from a Phase 1/2 study in adult smokers. The primary outcome standard deviation from this study was found to be approximately 17. Based on this standard deviation, the estimated between-arm differences in the primary comparisons can be estimated with a 95% CI that is ± 8.3 .

The trial size will not have sensitivity for a dichotomous outcome (e.g. smoking cessation as one of the other efficacy outcomes), other than for possibly large differences. For example, if the control arm outcome is 12% (3/25 defined as successes), then the experimental arm will have a two-sided 95% CI for the probability difference that excludes zero when the success probability is 36% (8/50) or more (computation based on exact CI).

3.6. Treatment Assignment

A total of approximately 250 subjects who meet the inclusion/exclusion criteria will be randomized at 2:1 ratio to the cytisine treatment and the respective placebo treatment as designated by the defined schedule, commercial titration vs simplified tid schedule.

3.7. Administration of Study Medication

All subjects will receive 2 tablets at each dosing according to the commercial titration schedule or to simplified tid schedule. For details, refer to the protocol.

4. EFFICACY AND SAFETY ENDPOINTS

4.1. Efficacy Endpoints

Efficacy endpoints will be based on cigarette consumption data. Subjects will record their cigarette consumption in a daily diary for 7 consecutive days during the screening period, and each day during the 25-day treatment period (i.e. on Day 1 through Day 25, inclusive). After Day 25, subjects will attend a Day 27 End of Treatment (EOT) clinic visit and post-treatment follow-up visits at Week 5, Week 6, Week 7 and Week 8. At each visit clinic staff will ask subjects whether they have smoked since the previous clinic visit and/or over the past 7 days, and the number of cigarettes smoked in the past 7 days.

4.1.1. Primary Efficacy Endpoint

The primary efficacy endpoint will be based on the daily cigarette consumption data recorded in the subject diary. The primary efficacy endpoint is defined as the percent of expected cigarettes smoked computed for each subject, at end of treatment. This percent is designated by Y, Y is calculated as below:

$$Y = \frac{100 \times N}{T \times R}$$

where N represents total number of cigarettes smoked each day over the treatment period from Day 1 to Day 25; T represents number of post-randomization days where number of cigarettes smoked is recorded; and R represents the average number of cigarettes smoked daily over the 7-day screening period as baseline. T*R represents the total number of cigarettes that would have been smoked without intervention over the number of recorded days.

If a subject has no cigarette-count data collected post-randomization, then the primary endpoint will be imputed to a value of 100 (i.e., no change from baseline cigarette consumption). This is equivalent to imputing the total number of post-randomization days with data recorded (T) is 25 and the total number of cigarettes smoked over the treatment period (N) is the average number smoked daily at baseline (R) times 25.

The primary comparisons for this endpoint will be comparisons of active arms to the associated placebo arm, refer to [Figure 1](#):

Arm A (1.5 mg cytosine commercial schedule) versus Arm C (placebo commercial schedule),
Arm B (3.0 mg cytosine commercial schedule) versus Arm C (placebo commercial schedule),
Arm D (1.5 mg cytosine tid schedule) versus Arm F (placebo tid schedule), and
Arm E (3.0 mg cytosine tid schedule) versus Arm F (placebo tid schedule).

4.1.2. Other Efficacy Endpoints

The endpoints associated with the other efficacy objectives are:

Abstinence from Week 5 to Week 8 is a binary endpoint (success, failure). Success is defined for a subject as having reported smoking abstinence (no cigarettes since the last clinic visit and over the past 7 days) at each clinic assessment from Week 5 to Week 8 with biochemical verification at each assessment. Biochemical verification will be defined by a CO concentration in exhaled breath of less than 10 ppm. Subjects will be allowed only 1 missed visit (smoking status and/or biochemical verification status unknown) between Week 5 and Week 8 (i.e. one of Week 6 or Week 7 visits only) for analysis of the abstinence from Week 5 to Week 8 endpoint.

Any outcome other than success will be regarded as a failure. There are therefore two types of failure for subjects: (1) subjects with adequate data that they were smoking at any time from Week 5 to Week 8 (either by the subject's self-report of smoking or CO \geq 10 ppm) and (2) subjects having insufficient data to be determined as a success for abstinence from Week 5 to

Week 8 endpoint (e.g., subjects lost to follow-up, missing the Week 5 and/or Week 8 clinic visit, or missing both the Week 6 and Week 7 visits).

All subjects will have a realization of this endpoint, thereby enabling analyses that follow the intent-to-treat (ITT) principle without imputation.

Initial quit rate is a binary endpoint (success, failure) at Week 4 (Day 27 EOT). Success is defined for a subject as having reported smoking zero cigarettes in the subject diary at Day 25, with biochemical verification by an expired-air CO reading <10 ppm at the Day 27 EOT clinic visit. Any other outcome will be regarded as a failure. This endpoint is defined at the End of Treatment visit so that subjects have approximately a 2½-week grace period after the Day 5-7 quit date. All subjects will have a realization for this endpoint, thereby enabling analyses that follow the ITT principle without imputation.

7-day point prevalence is a binary endpoint (success, failure) at each of the following visits: Week 5, Week 6, Week 7 and Week 8. At each visit, success is defined for a subject as having reported not smoking any cigarettes over the past 7 days with biochemical verification by an expired-air CO reading <10 ppm. Any other outcome will be regarded as a failure. All subjects will have a realization of this endpoint, thereby enabling analyses that follow the ITT principle without imputation.

Time to failure to maintain abstinence through Week 8 will be evaluated for the subgroup of subjects who were classified as a success for the initial quit rate endpoint (see previous definition). Time to failure to maintain abstinence (days) will be calculated as end date of abstinence minus start date of abstinence + 1. The start date of abstinence will be defined as the date of the Week 4 (Day 27 EOT) visit. The end date of abstinence will be defined as the earliest date that the subject was known to have resumed smoking. Specifically:

- At a visit, if a subject reported not smoking in the past 7 days but has smoked since the last visit (either by the subject's self-report or $CO \geq 10$ ppm), the end date of abstinence will be the date of that last visit.
- At a visit, if a subject reported not smoking since the last visit but has smoked in the past 7 days (either by the subject's self-report or $CO \geq 10$ ppm), the end date of abstinence will be defined as the date of the visit minus 7 days.
- Subjects who have not resumed smoking at the final (Week 8) visit will have end date of abstinence censored at the date of the Week 8 visit.

Relationship between Outcome Variables and Smoking Reduction and Cessation

Endpoints: The relationships between subject-reported outcomes (e.g. anxiety, depression, withdrawal symptoms, tobacco craving, alcohol use) and the following smoking efficacy endpoints will be evaluated:

- The primary efficacy endpoint, which measures reduction in smoking during the study treatment period.
- Initial quit rate, which evaluates smoking cessation at Week 4 (Day 27/EOT).

- Abstinence from Week 5 to Week 8.

It is expected that the relationship between each of these efficacy variables and the following subject-reported outcome variables will be evaluated for this objective:

- Change during the treatment period, in self-reported number of cigarettes smoked over the previous 24 hours.
- Total scores and change from baseline for the following questionnaires: HADS-Anxiety, HADS- Depression, Tobacco Craving (TC).
- TC subscores for Emotionality, Expectancy, Compulsivity, and Purposefulness.
- Responses on the Alcohol Use questionnaire.
- Adverse event outcomes such as whether the subject experienced any adverse events, any serious adverse events.
- Compliance outcomes such as percent of study drug taken, number of behavioral support sessions attended.

The potential correlation for subjects' nicotine metabolite ratio (NMR) with both reduction in cigarette use and smoking cessation will be explored during the study treatment period and at Week 8.

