6.3.1. Missing Dates

Partial or missing dates will be imputed only if a date is required to derive a study endpoint (e.g. time to failure, duration of AE). Otherwise no date imputation will be done. Date imputation will follow the rules below.

Efficacy Related Dates

Partial or missing dates required to computing efficacy endpoints will be imputed as follows:

- **Missing day only:** For partial dates with only the day of the month missing, the day will be imputed as the 15th day of the month, provided that a preceding date of interest does not occur in the same month. If the preceding date does occur in the same month, then the missing day will be imputed as half the distance between the preceding date and the end of the month.
- **Missing month and day:** For partial dates with the month and day missing, the month and day will be imputed as July 1st, provided that a preceding date of interest does not occur in the same year. If the preceding date occurs in the same year, then the month and day will be imputed as half the distance from the preceding date to the end of the known year.
- **Missing month, day, and year:** Missing dates will be imputed as the date of first dose.
- **In situations where the above rules result in an illogical time (e.g., negative study day, negative time to failure, etc) the date will be imputed as the date half the distance between the preceding date of interest and the partial date.**

Safety Related Dates

For safety data where the date of onset is during or after administration of the first dose of study drug, missing or partial start dates will be imputed as the earliest possible date that is on or after the date of the first dose of study drug. For events occurring prior to first dose of study drug, missing or partial dates will not be imputed.

- Missing day only: If the start date and date of first dose share the same month and year, the missing start day will be imputed as the day of first dose. If the start date month is after the month of first dose, day will be imputed as the 1st (i.e., 01-Jan-2019).
- Missing month and day: If the start date and date of first dose share the same year, day and month will be imputed as the day and month of first dose. If the start date year is after the year of first dose, the month and day will be imputed as January 1st (i.e., 01-Jan-2019).
- Missing month, day, and year: Missing start dates will be imputed as the date of first dose.

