10.2.3. Initial Quit Rates

The initial quit rate endpoint is binary (success, failure) defined at Week 4 (Day 27 EOT). For each comparison (see [Section 10.2](#)), the treatment arms will be compared in terms of the proportion of subjects classified as a success ([Section 4.1.2](#)). The effect size estimate of each comparison will be based on the common odds ratio estimate using exact computations for stratified 2x2 frequency tables.

If there is evidence of odds ratio heterogeneity across the strata (p-value for Zelen's Exact Test ≤ 0.10) then the analysis will be performed separately for each level of the stratification factor and stratum-specific estimates of the odds ratios and their 95% CIs will be reported.

10.2.4. 7-day Point Prevalence

The 7-day point prevalence endpoints are binary (success, failure) endpoints defined at each of the following visits: Week 5, Week 6, Week 7 and Week 8.

For each comparison (see [Section 10.2](#)), the treatment arms will be compared in terms of the proportion of subjects classified as a success ([Section 4.1.2](#)). The effect size estimate of each comparison will be based on the common odds ratio estimate using exact computations for stratified 2x2 frequency tables.

If there is evidence of odds ratio heterogeneity across the strata (p-value for Zelen's Exact Test ≤ 0.10) then the analysis will be performed separately for each level of the stratification factor and stratum-specific estimates of the odds ratios and their CIs will be reported.

10.2.5. Time to Failure to Maintain Abstinence Through Week 8

Time to failure to maintain abstinence through Week 8 ([Section 4.1.2](#)) will be evaluated for the subgroup of subjects who were classified as a success on the initial quit rate endpoint. Time to failure (days) will be calculated for individual subjects as described in [Section 4.1.2](#). Subjects who are still abstinent at Week 8 will have time to failure censored at the date of the Week 8 visit.

Time to failure will be summarized by treatment arm; the minimum, maximum, median and 95% confidence interval for the median time to failure reported by the LIFETEST procedure will be reported. Two Kaplan-Meier figures of treatment arm by time to failure will be produced, one figure for each schedule (commercial, tid).

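### The SAP's dating rules for time to failure neither cover every case nor exclude each other, and within the permitted visit windows one of them can return zero or negative times

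*SAP*

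**What the plan says.** SAP 4.1.2 restricts time to failure to subjects who were successes on initial quit rate (zero cigarettes on Day 25 and CO below 10 ppm at EOT). The time is "calculated as end date of abstinence minus start date of abstinence + 1". On the start: "The start date of abstinence will be defined as the date of the Week 4 (Day 27 EOT) visit". On the end: "The end date of abstinence will be defined as the earliest date that the subject was known to have resumed smoking". Three specific rules follow.

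- **Rule 1.** "At a visit, if a subject reported not smoking in the past 7 days but has smoked since the last visit", by self-report or CO of 10 ppm or more, then "the end date of abstinence will be the date of that last visit".
- **Rule 2.** No smoking reported since the last visit, but smoking in the past 7 days, again by self-report or CO: "the end date of abstinence will be defined as the date of the visit minus 7 days".
- **Rule 3.** Subjects who have not resumed by the Week 8 visit are censored on that date.

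SAP 10.2.5 repeats the Week 8 censoring and adds: "Time to failure will be summarized by treatment arm", with medians, confidence intervals and Kaplan-Meier plots. It names no between-arm estimate, although objective 3 (SAP 3.2) is to compare the arms and SAP 10.2 lists four within-schedule comparisons for each of these endpoints.

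At each follow-up visit (protocol 12.2.4) the site records whether the subject smoked since the last visit (yes/no), whether they smoked in the past 7 days (yes/no), an average daily count if they smoked, and CO. No resumption date is collected.

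**The concern.** The two yes/no answers and the CO reading define a small set of patterns, and each should lead to exactly one date. Here one pattern can lead to an impossible duration, one leads to two dates, one leads to none, and subjects who leave early are not mentioned. This is the only analysis planned for objective 3. If the rules stay as they are, the programmer must choose the missing dates, and two competent programmers could draw different curves from the same data.

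**Working it through.** The documents give no sample size, event count or precision for this endpoint, so there is no stated figure to reproduce. The check applies the SAP formula to every permitted pair of visit days.

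**Inputs**

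- EOT visit, day E: Day 27 ± 2, so 25 to 29 (SAP 2.1). The first footnote to protocol Table 10 instead says Day 25 to 27.
- Follow-up visits, day V: ± 3 days (protocol 7.1). *Assumption:* Week k is Day 7k, so Week 5 is Day 35 with window 32 to 38. The synopsis supports this: 8 weeks is put at about 31 days after treatment, and 25 + 31 = 56 = 8 × 7.
- Gap: days from the previous visit to the current one.

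**(a) Rule 2 at Week 5**

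Time = (V - 7) - E + 1 = gap - 6.

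The gap runs from 32 - 29 = 3 to 38 - 25 = 13.

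| Gap (days) | Day pairs | Time (days) |
|---|---|---|
| 3 | 1 | -3 |
| 4 | 2 | -2 |
| 5 | 3 | -1 |
| 6 | 4 | 0 |

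That is 1 + 2 + 3 + 4 = 10 of 5 × 7 = 35 pairs. With EOT limited to Day 25 to 27 it is 3 of 21, with a minimum of 5 - 6 = -1. On nominal days the gap is 35 - 27 = 8 and the time is +2. From Week 6 on the minimum is (39 - 7) - 29 + 1 = +4, so non-positive times arise only at Week 5.

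By consistent self-report, rule 2 needs smoking within 7 days but before the last visit, hence a gap of about 7 days or less. At Week 5 that route can return no more than 7 - 6 = 1 day. Longer times under rule 2 come through the CO route.

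**(b) No to both questions, CO of 10 ppm or more**

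Both rules apply. Rule 2 date minus rule 1 date = gap - 7.

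- Nominal Week 5: 8 - 7 = +1 day.
- Nominal Weeks 6 to 8: 7 - 7 = 0 days.
- Window extremes: -4 to +6 days at Week 5 (gap 3 to 13); -6 to +6 days later (gap 1 to 13).

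**(c) Yes to both questions**

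Rule 1 needs a no to the 7-day question and rule 2 a no to the other, so neither applies. At an exact 7-day spacing both questions cover the same days, so a subject who relapsed and answers consistently says yes to both. Candidate times on nominal days:

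| Visit | From last visit | From visit minus 7 | From visit | Spread |
|---|---|---|---|---|
| Week 5 | 1 | 2 | 9 | 8 |
| Week 6 | 9 | 9 | 16 | 7 |
| Week 7 | 16 | 16 | 23 | 7 |
| Week 8 | 23 | 23 | 30 | 7 |

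**(d) Lost before Week 8 with no recorded relapse**

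Rule 3 needs a Week 8 visit. Take a subject last seen abstinent at nominal Week 6. The time could be censored at 42 - 27 + 1 = 16 days, failed at 16 days, or failed at the missed Week 7 visit at 49 - 27 + 1 = 23 days. The SAP does not choose.

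**Does SAP 6.3.1 repair this?**

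For illogical times, including negative time to failure, it says "the date will be imputed as the date half the distance between the preceding date of interest and the partial date". That clause belongs to the rules for partial or missing dates. Visit minus 7 is a complete date, so there is no partial date to work from. For a wholly missing date the fallback is first dose (Day 1), which gives 1 - 25 + 1 = -23 to 1 - 29 + 1 = -27 days.

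**The case against.** The best defence is that the general sentence governs: failure is the earliest date on which smoking is known to have resumed, and the rules below it are illustrations. On that reading, earliest breaks the tie in (b), and the subject in (c) plainly counts as a failure. On nominal days the two rules' dates agree to within one day, and the Week 5 time under rule 2 is a valid +2. The self-report route to a non-positive time is also narrow: the subject must have passed the initial-quit test and then report smoking within 7 days but not since EOT. For lost subjects, protocol 13 treats them as not having quit, and SAP 6.3 keeps dropouts in the analysis as far as their data allow.

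Much of this stands, and it limits what can be claimed. A reader might infer that 10 of 35 means 29% of subjects would get impossible times. The documents do not support that, since it counts permitted day pairs and nothing is said about how visits fall within the windows. A reader might also infer that relapses or all dropouts would vanish from the curves. That does not follow either: a subject with a dated relapse before loss already has an event, and the yes/yes subject is a failure under the general definition. Nor is a Week 6 to 8 failure dated before the previous visit always wrong. If a later answer contradicts an earlier one, the earliest-date principle can require it.

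The defence does not close the gaps. With a gap under 7 days, the earliest-date tie-break selects visit minus 7, which precedes a visit at which the subject was classed abstinent and at Week 5 is the non-positive time itself. The general sentence cannot fix a date for (c) because no resumption date is collected. Protocol 13 gives lost subjects a status but no date, and SAP 10.2.5 does not say whether they are events or censored.

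**Conclusion.** The concern holds in this limited form. Followed literally, a written rule returns 0 to -3 days for some permitted visit timings, one answer pattern has two dates, and two situations have none. The size ranges from nothing or one day on nominal days for the pattern with two dates, through 7 to 8 days for the yes/yes relapse, to an open choice between event and censoring for lost subjects. All of this is on a horizon of about 30 days (56 - 27 + 1). The day-pair counts rest on Week 5 being Day 35 and on which EOT window applies; the logical gaps in (b) to (d) rest on neither.

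The consequence is modest. Time to failure is not among the key endpoints in SAP 6.5, it is summarised descriptively in a subgroup, and SAP 6.1 plans no formal hypothesis testing. The primary endpoint and Week 5 to 8 abstinence are unaffected. It should be corrected because it is the only analysis of a stated objective and the correction is cheap.

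**What to change.** Replace the rules in SAP 4.1.2 with a single one:

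- **Event.** Failure is any self-reported smoking, on either question, or CO of 10 ppm or more at an attended visit.
- **Date.** Use one convention for every pattern, for example the midpoint between the last attended verified-abstinent visit and the failing visit, or the date of the failing visit. It must never precede the EOT visit.
- **Missed visits.** A single missed Week 6 or Week 7 visit followed by a verified-abstinent visit is not a failure, matching the tolerance in the Week 5 to 8 abstinence endpoint. State the handling of a missed Week 5 visit and of two missed visits in a row.
- **Lost subjects.** For those lost before Week 8 without a recorded relapse, count failure at a fixed, stated date after the last verified-abstinent visit, in line with protocol 13. Censor at that last visit as the sensitivity analysis.
- **Comparison.** In SAP 10.2.5, add the difference in the Kaplan-Meier proportion still abstinent at Week 8, with a 95% confidence interval, for the four within-schedule comparisons.

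The cost is SAP wording and a few lines of derivation code on data already collected. Dates will be accurate only to the visit interval, which is already the case. The choice of convention is partly a matter of preference; what matters is fixing it before unblinding.
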